4.9.10 Exploratory objectives

1) Describe the changes with time in likelihood of developing HZ after laboratory-confirmation of SARS-CoV2.

A descriptive analysis (including Means, standard deviations, quartiles and ranges) of the time to the HZ incident case after Sars-Cov-2 diagnosis will be summarized overall and stratified by age, sex, frailty category, and comorbidity and Sars-Cov-2 severity.

Analyses of the anonymised data will be carried out using R Statistical Software version 4.1.1 (Foundation for Statistical Computing, Vienna, Austria).

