3.3 Exploratory objectives

Describe the changes with time in likelihood of developing HZ after laboratory-confirmation of SARS-CoV2.

4. Methods

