4.2 Study population and period

The cohort will include all subjects older than 18 years living in Valencia Region, registered in the Regional Health System (RHS) (over 98%) from January 1st 2018 to, at least, December 31st 2020 (or date of data extraction). The inclusion and exclusion criteria will be the following:

Inclusion criteria: Subjects aged 18 years and above covered by the RHS and residing in the Valencia Region during study period.

Exclusion criteria:

- Subjects with less than 12 months of registration to the RHS and subjects with incorrect codification.
- Subjects vaccinated against HZ before the diagnosis of SARS-CoV-2
- Subjects vaccinated against SARS-CoV-2 before the diagnosis of SARS-CoV-2

Start of follow-up: The start of the follow-up is defined as the latest of start of the study (1st January 2018), first date of registration in the database or date of the 18th birthday.

End of follow-up: The end of the follow-up is defined as the earliest of the following cases:

- End of study period
- Loss of follow-up (exit of RHS)
- Exitus
- Vaccination with HZ vaccine
- Vaccination with COVID-19 vaccine
- Development of HZ

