4.4 Sars-Cov-2 exposure

Exposure status of everyone might change within the follow up period (Figure 3): Sars-Cov-2 unexposed in the pre-pandemic period and Sars-Cov-2 exposed in the pandemic period. Sars-Cov-2 exposure levels will be treated as a time-varying variable and the following states will be considered:

- 1) **Sars-Cov-2 unexposed**: subject's follow up period from the start of follow-up to the declaration of the pandemic in Spain (March 14th 2020).
- 2) **Sars-Cov-2 exposed**: subject's follow up period from the start of the pandemic. We will consider the following 2 comparison groups:
 - **Sars-Cov-2 free**: time from the start of pandemic (or the follow-up) to the date of the first Sars-Cov-2 confirmation (by PCR or Ag test). If no Sars-Cov-2 positive test registered, the time period will be until the end of follow-up.
 - **Sars-Cov-2 laboratory-confirmed**: time from the date of the SARS-CoV-2 positive result in RedMiva to the end of follow up.

[figure not shown]

Figure 3. Example of exposure, follow-up and comparisons in the study.

* Subjects with recurrent episodes of Sars-Cov-2 will be treated separately. If the sample size is not large enough for the analysis, these individuals will be excluded for the analysis.

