4.9.4 Number of tests performed in The Region over time

As of December 31st 2020, a total of 2.112.504 SARS-CoV-2 tests were performed. The following table shows the monthly number of positive and negative tests (both PCR and Ag) performed.

			Negative	results		Positive results					
Month	Total tests	Total negatives	% of total	AG	PCR	Total	% of total	AG	PCR		
feb-20	514	468	91,05058366		468	46	9,829059829		46		
mar-20	39403	26394	66,98474735		26394	13009	49,28771691		13009		
abr-20	80998	69783	86,15397911		69783	11215	16,07124944		11215		
may-20	114973	112264	97,64379463		112264	2709	2,413062068		2709		
jun-20	101371	100395	99,03719999		100395	976	0,972159968		976		
jul-20	133709	128809	96,33532522		128809	4900	3,804082013		4900		
ago-20	243498	216819	89,04344184		216819	26679	12,30473344		26679		
sept-20	269026	240845	89,52480429	912	239933	28181	11,74536225	109	28072		
oct-20	305193	255984	83,87610463	11170	244814	49209	20,10056614	4832	44377		
nov-20	394144	323865	82,16920719	44718	279147	70279	25,17634078	14560	55719		
dic-20	429675	348567	81,12340723	67192	281375	81108	28,82558863	20070	61038		
Total 2020	2112504	182/103	86 35216785	123002	1700201	288311	16 957/6562	30571	2/87/0		

4.9.5 Power Calculation for HZ IR comparison among SARS-Cov-2 labconfirmed and SARS-Cov-2 free.

Considering an HZ IR of 7 cases per 1000 persons-year in SARS-Cov-2 free, and the following expected populations: 110 000 SARS-Cov-2 lab-confirmed and 2 000 000 SARS-Cov-2 free, we would be able to find statistically significant (significance level = 0.05) differences in RR for HZ (SARS-Cov-2 free vs. Lab-confirmed) of 10% (RR 1.1) with a power of ~ 80% (power = 0.760864).

Power calculation was estimated based on the Two-sample Poisson Ratio Tests (Different Sizes) from the PASSED package of R (version 4.0.2).

Statistical analysis

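### Section 4.9.10 summarises time to HZ among cases only, so with no denominator or censoring it mixes HZ risk with follow-up length and cannot alone describe how likelihood changes after infection

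*Protocol*

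**What the plan says.** Section 3.3 sets the objective: "Describe the changes with time in likelihood of developing HZ after laboratory-confirmation of SARS-CoV2". Section 4.9.10 repeats it and gives one analysis: "A descriptive analysis (including Means, standard deviations, quartiles and ranges) of the time to the HZ incident case after Sars-Cov-2 diagnosis will be summarized". This summary is to be given for all cases together and within categories of age, sex, frailty, comorbidity and severity.

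The time available after infection is fixed elsewhere:

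- Section 4.4 defines laboratory-confirmed time as "time from the date of the SARS-CoV-2 positive result in RedMiva to the end of follow up".
- Section 4.2 gives the study period as "from January 1st 2018 to, at least, December 31st 2020 (or date of data extraction"), so the end date is a minimum.
- Section 4.2 also ends follow-up at leaving the health system, death, HZ vaccination and "Vaccination with COVID-19 vaccine".

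Two neighbouring sections bear on the question. Section 4.9.8 splits person-time by calendar time, age and comorbidity, but not by time since infection, and plans exact Poisson intervals for rates. Section 4.9.9, item 3, plans predicted probabilities of HZ within 1, 3 and 6 months of infection from logistic regression, under the severity objective.

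**The concern.** A statement about likelihood needs a denominator: the people, or the person-time, at risk in each period after infection. Time to HZ among cases has none. An event at 200 days can be seen only in someone followed for 200 days, so the distribution of observed times depends on the follow-up distribution as well as on the HZ rate. Here follow-up is uneven, because it depends on when each person tested positive, on an open study end and on several censoring events.

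A reader of the final report could therefore take a short median as a sign of early excess risk, or a long one as a sign of late risk, when either may reflect the extraction date. Differences between strata can arise in the same way wherever infection dates, mortality or vaccination timing differ. At stake is the interpretation of the exploratory objective. The primary and secondary comparisons do not use this summary.

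**Working it through.** **The plan's own figures.** Section 4.9.10 states none. The protocol's one design figure is the power in section 4.9.5 (0.760864), for "110 000 SARS-Cov-2 lab-confirmed and 2 000 000 SARS-Cov-2 free" subjects, "Considering an HZ IR of 7 cases per 1000 persons-year in SARS-Cov-2 free" and RR 1.1. Assuming one person-year per subject and a two-sided 0.05 score test:

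- Difference: 0.0077 − 0.0070 = 0.0007.
- Pooled rate: (110,000 × 0.0077 + 2,000,000 × 0.0070)/2,110,000 = 0.0070365.
- Null SE: √[0.0070365 × (1/110,000 + 1/2,000,000)] = 0.000260.
- Alternative SE: √(0.0077/110,000 + 0.0070/2,000,000) = 0.000271.
- Power: Φ[(0.0007 − 1.96 × 0.000260)/0.000271] = 0.759.

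That agrees with the stated value. The present point does not depend on it.

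**Inputs for the illustration.**

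- Entry times: monthly positives in section 4.9.4, February to December 2020: 46; 13,009; 11,215; 2,709; 976; 4,900; 26,679; 28,181; 49,209; 70,279; 81,108 (sum 288,311). These are positive tests at all ages, not unique adults, so only the calendar shape is used, spread evenly within months.
- HZ rate: constant at 7 per 1000 person-years, λ = 0.007/365.25 per day.
- Cut-off: 31 December 2020 (the stated minimum), with 30 June and 31 December 2021 as assumed alternatives. No infections after 2020 and no censoring before the cut-off.

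**Shape of follow-up at 31 December 2020.**

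- October to December: (49,209 + 70,279 + 81,108)/288,311 = 69.6% of positives.
- At least 90 days of follow-up: positive by 2 October, (87,715 + 2/31 × 49,209)/288,311 = 31.5%.
- At least 180 days: positive by 4 July, (27,955 + 4/31 × 4,900)/288,311 = 9.9%.

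**Case-only distribution.** Let R(t) be the number whose potential follow-up exceeds t days. The density of t among observed cases is proportional to λ·exp(−λt)·R(t). HZ is rare, so exp(−λt) stays close to 1 (about 0.994 at 335 days) and the density is nearly R(t)/∫R. Under a flat rate, the case-only summary essentially reproduces the follow-up curve.

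| Cut-off, flat rate | Quartiles (days) | HZ cases within 30 d | within 90 d |
|---|---|---|---|
| 31 Dec 2020 | 22/53/106 | 32% | 69% |
| 30 Jun 2021 | 65/131/198 | 12% | 34% |
| 31 Dec 2021 | 111/223/334 | 7% | 20% |

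Counting conventions for the first and last day move these by about one day. At the first cut-off the shares come from person-years: 20,344/63,278 = 32% and (20,344 + 23,560)/63,278 = 69%.

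**By infection date.** With the same flat rate and the December 2020 cut-off, the median is about 137 days for March–April infections and 17 days for November–December infections.

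**Can the summary separate risk from follow-up?** If the rate truly doubles in the first 30 days, the quartiles are about 14/31/84 days at 31 December 2020 and 42/115/188 at 30 June 2021. So risk does move the summary. Yet the second median, with a real early excess, is later than the flat-rate median of about 53 days at the earlier cut-off.

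**With a denominator.** Flat rate, 31 December 2020, events/person-years by days since infection:

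- 0–30: 142.4/20,344 = 7.0 per 1000
- 30–90: 164.9/23,560 = 7.0
- 90–180: 88.3/12,612 = 7.0
- over 180: 47.3/6,762 = 7.0

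Rates by interval return the flat truth. With the first-30-day rate doubled, they return 14.0 and then 7.0, at either cut-off.

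**The case against.** - **The study looks at time since infection elsewhere.** The 1-, 3- and 6-month cumulative incidences in section 4.9.9 have a denominator and show how likelihood accrues. This stands: it would be wrong to infer that section 4.9.10 is the only planned look. But those estimates are assigned to the severity objective, and the protocol does not say how people followed for less than the window enter the logistic model. At the December 2020 cut-off only about 10% would have 180 days.
- **The earliest cut-off is the extreme case.** The study end is a minimum, and the timeline, as far as the table can be read, marks data extraction in July 2021, October 2021 and January 2022. This also stands. A reader might infer that the report would show HZ clustered soon after infection whatever the truth. The later cut-offs above do not support that. Infections in 2021 and censoring at vaccination could shorten follow-up again, but the documents give no figures for either.
- **Stratum comparisons need not be distorted.** Correct: distortion arises only where follow-up differs between strata, and the documents give no infection dates by stratum. Nor does the summary reflect follow-up alone, as the doubled-rate example shows.
- **The objective is exploratory and descriptive.** True, and this limits the consequences. The rationale mentions lymphopenia without a time course, and nothing assigns this analysis to test that mechanism. The label does not supply the missing denominator.

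**Conclusion.** The concern holds as a mismatch between objective and analysis. A case-only summary of time to HZ, with no person-time and no handling of censoring, does not describe change in likelihood; it mixes risk with follow-up length at any cut-off. Its size depends on the extraction date: under a flat rate the median runs from about 53 to about 223 days across the three cut-offs.

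These figures rest on all-age positive tests used only for their calendar shape, 2020 infections only, even entry within months and no censoring before the cut-off. The assumed HZ rate hardly affects the timing. Certain early clustering is not established, and the primary and secondary results are untouched. The change is worth making, but its importance is limited to an exploratory objective.

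**What to change.** In section 4.9.10, add time since the positive result (for example 0–30, 31–90, 91–180 and over 180 days) to the person-time split of section 4.9.8. Report HZ rates per 1000 person-years by interval with the exact Poisson intervals already planned there, overall and, where event counts allow, by the listed strata. Adjusted RRs against SARS-CoV-2-free time, overall, are optional. Keep the case-only summary as a supplement, presented beside the follow-up distribution.

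The cost is one more split variable and one more table, with no new data. The drawback is sparse cells in later intervals if the cut-off is early. Scaling the flat-rate events above to the 119,935 cases over 50 in section 4.9.3 (119,935/288,311 = 0.416) gives roughly 59, 69, 37 and 20 events in the four intervals before any stratification. Full stratification by interval would therefore be thin at the December 2020 cut-off, and the descriptive objective does not need it.

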4.10 Limitations

Potential limitations of the VID have been described elsewhere (27). Data quality may be a strength in some databases, but also a weakness in other repositories or for certain data, such as incompleteness of early data from Accident and Emergency Department (AED) records. Also, we do not have information about people that are not in contact with the public healthcare service or who are attended to in the private sector.

Clinically-diagnosed SARS-CoV-2 or asymptomatic cases without laboratory confirmation will be considered as SARS-CoV-2 free in the study. Nevertheless, Public Health surveillance for Covid-19 team guarantees that that percentage must be insignificant.

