Abucasis SIA-GAIA (Ambulatory Information System - Care provision management) is a primary care database used across the entire Valencia healthcare system that contains medical information for each patient attended in the Primary Care (PC) setting (General Practitioners, GPs, and specialists). It was set up in 2006 and the percentage of the population included increased from 73.1% in 2007 to 88.8% in 2008 and to 95.7% in 2009. This database contains primary care diagnoses (physician coded using the International Classification of Diseases Revision, Clinical Modification (ICD-CM)) and all drug prescriptions (using Anatomical Therapeutic Chemical (ATC) Classification System). In addition, the physician or paediatrician and nurse responsible recorded text about each episode and about the patient is included. The database is also used at Specialty Centres and is considered reliable since 2007.

Hospital Discharge Database

The Spanish hospital discharge database, MBDS (Minimum Basic Data Set), collects diagnosis and procedures as an assessment of medical activity. The coding system used is ICD-9-CM until 2016 and ICD-10-CM afterwards. The main discharge diagnosis is coded in first position, and diagnosis relevance decreases as the position number increases. Using MBDS is compulsory for all public hospitals, and over 95% of all discharges are included. According to the Spanish Ministry of Health, data are considered reliable since 2002.

Microbiological Surveillance Network

The Microbiological Surveillance Network (RedMIVA) contains all the results (positive or negative) given by all the microbiology laboratories of the Valencian Public System network. All data is transferred from the laboratories to the RedMIVA database on a daily basis. Data are considered reliable since 2008.

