3.1. LIST OF VARIABLES TO BE EXTRACTED FROM DATABASES

Data privacy will be protected by using anonymised data (see 2.2. section). The following variables will be requested to the different databases for the period from 1 January 2007 to 31 January 2015 for subjects \geq 18 years old:

Data to be extracted from SIP:

- Identification block including SIP number, sex, date of birth and other geographical of birth, place and date of registration (excluding identifying data as surnames, ID card number, phone numbers, etc.)
- Assignation block (including municipality, healthcare district, etc)
- Regular location block that includes complete address, health map information as health department and census information among others (excluding exact data that allows the exact residence location of the subjects)
- Cessation block including cessation cause and description, cessation date and date of death (when applicable)
- APSI code
- Barthel Index

Data to be extracted from SIA

- SIP number

Morbidity database

- Date of diagnosis activation (diagnosis of interest)
- Date of diagnosis deactivation (diagnosis of interest)
- Diagnosis description (diagnosis of interest)
- ICD-codes (diagnosis of interest)

Outpatient visits database

- Date of the visit
- Diagnosis description
- ICD-code

Specialist visits database

- Date of the visit
- Diagnosis description
- ICD-code
- Professional attendance (GP/Specialist)
- Specialist service

For any diagnosed code related to HZ (see section 4.3) and comorbidities (see section 4.6.3)

Data to be extracted from MBDS:

- Anonymized Personal Identification Number (SIP)
- Birth date
- Sex
- Municipality of residence
- Postal code
- Health department
- Health care district
- Date of hospital admission
- Date of hospital discharge
- Diagnoses at discharge (main and secondary diagnoses)
- Procedures during the hospitalization
- Discharge destination (destination on discharge)
- ICU (any position)
- POA

For any diagnosed code related to HZ (see section 4.3) and comorbidities (see section 4.6.3) and SARS-Cov-2 (J12.89, J20.8, J40, J22, J98.8, J80, R65.20, R65.21, R05, R06.02, R50.9, R43.0, Z20.828, Z03.818, Z11.59 O98.5, B97.29 or U07.1 and B34.2)

Data to be extracted from RedMIVA

- SIP number
- Date of laboratory test (dd/mm/yyyy)
- Date of test result
- Sample type
- Laboratory test (PCR, antigen, etc)
- Result

For any SARS-Cov-2 test

Source	Dataset	Variable	Label	Туре	Coding

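### HZ may be recorded more completely in lab-confirmed subjects than in the SARS-CoV-2-free comparator, which could bias the primary RR upward by an unknown amount; a test-negative sensitivity comparison would check this.

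*Protocol*

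**What the plan says.** - **Exposed group (section 4.4).** Lab-confirmed time starts at a positive result in RedMIVA. Section 4.7.1 describes RedMIVA as holding the results "given by all the microbiology laboratories of the Valencian Public System network".
- **Comparator (section 4.4).** SARS-CoV-2-free time ends at a first positive, and otherwise: "If no Sars-Cov-2 positive test registered, the time period will be until the end of follow-up". No negative test or other contact is required. Entry depends on coverage and residence (4.2), and the population is taken from the SIP administrative file (4.12).
- **Outcome (section 4.3).** HZ cases are taken from SIA (outpatient) and MBDS (inpatient).
- **Adjustment (section 4.9.6).** The primary model considers age, sex and comorbidities. Comorbidities are themselves identified from MBDS or SIA (4.6.3).
- **Stated limitation (section 4.10).** The study lacks information on "people that are not in contact with the public healthcare service or who are attended to in the private sector". No size is given, and the limitation is not related to exposure group.
- **Tests requested (Annex 1).** RedMIVA dates and results are requested "For any SARS-Cov-2 test", so negative results are included.

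**The concern.** Every lab-confirmed subject has at least one documented contact with the public system. The comparator also holds registered people who make no use of public care, or who take their shingles to a private physician. They add person-time to the denominator, but their HZ cannot reach the numerator. If such people are a larger share of the free group than of the lab-confirmed group, the comparator's HZ rate is understated and the RR rises.

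The hypothesis in section 2 is that risk is higher after infection, so this error would run in the hypothesised direction. The planned adjustment does not remove it. A person who does not use public care has no recorded comorbidity and is placed among the healthy, so the gap in recording persists within strata.

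**Working it through.** **1. The plan's own figure.** Section 4.9.5 gives these inputs: "Considering an HZ IR of 7 cases per 1000 persons-year in SARS-Cov-2 free", populations of "110 000 SARS-Cov-2 lab-confirmed and 2 000 000 SARS-Cov-2 free", and "statistically significant (significance level = 0.05) differences in RR for HZ" "of 10% (RR 1.1) with a power of ~ 80% (power = 0.760864"). I take the test as two-sided and count one person-year per subject; the protocol states neither.

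- Expected events: 110,000 × 0.0077 = 847 and 2,000,000 × 0.007 = 14,000.
- SE of log RR = √(1/847 + 1/14,000) = 0.0354.
- z = ln(1.1)/0.0354 = 2.69. Power = Φ(2.69 − 1.96) = 0.768.
- Other two-sided versions give 0.759 (pooled variance) and 0.748 (exact conditional).

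The stated 0.760864 is reproduced to within about 2 points.

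**2. Bias under a true RR of 1.** Let q1 and q0 be the shares of HZ cases unseen among lab-confirmed and free subjects. Then

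observed RR = (1 − q1)/(1 − q0).

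Neither share is in the protocol. The coverage figure of over 98% concerns entitlement, not use, and does not supply q0. All values below are assumptions.

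| q1 | q0 | Observed RR |
|---|---|---|
| 0 | 1% | 1.010 |
| 0 | 2% | 1.020 |
| 0 | 3% | 1.031 |
| 0 | 5% | 1.053 |
| 5% | 10% | 1.056 |
| 5% | 5% | 1.000 |
| 5% | 2% | 0.969 |

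The last row shows that the sign depends on which group is recorded less completely.

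**3. Effect on the test.** With q1 = 0 and no true effect, the expected events are 110,000 × 0.007 = 770 and 14,000 × (1 − q0).

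- q0 = 2%: SE = √(1/770 + 1/13,720) = 0.0370; ln(1/0.98) = 0.0202; shift 0.55 SE; two-sided rejection probability 8.5%.
- q0 = 5%: SE = √(1/770 + 1/13,300) = 0.0371; ln(1/0.95) = 0.0513; shift 1.38 SE; two-sided rejection probability 28%.

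The nominal level is 5%. These probabilities rest on one person-year per subject and would be lower with shorter follow-up. The bias in the RR would not change.

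**The case against.** **The size is not known, and a reader might infer too much.** An observed RR of 1.10 under the null would need q0 = 1 − 1/1.1 = 9.1% with q1 = 0, or about 10% against 1%. Nothing in the protocol supports such a gap. It would be wrong to say that the bias reaches the 10% design effect, or that 10% bounds it. The nearest figure is in section 4.7.1: the primary care database included 95.7% of the population in 2009. If the remaining 4.3% were non-users, the RR would be 1/0.957 = 1.045. That figure may describe database roll-out instead, and it says nothing about private care among people who are included.

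**The direction is expected, not established.** One public test does not show that a person's later shingles would be seen publicly, so q1 need not be 0. Section 4.9.4 reports 2,112,504 tests in 2020, so having been tested is weak evidence of habitual public care. Unconfirmed infections counted as free (4.10) also dilute any true effect. With a true RR of 1.1 and an assumed 10% of the comparator infected, the observed RR is 1.1/(1 + 0.10 × 0.1) = 1.089. Both points stand, and the net bias is unknown. Dilution does not cancel the ascertainment bias when the true RR is 1, however, and the protocol calls the unconfirmed share insignificant.

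**The blind spot is disclosed, and sensitivity analyses often belong in the SAP.** Using all SARS-CoV-2-free time is a recognised choice for a population cohort, and section 4.10 states nothing false. What remains is that the protocol itself fixes the comparator in 4.4 and names the adjustment variables in 4.9.6, and neither section deals with a difference in recording between the groups.

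**Conclusion.** The asymmetry follows from the protocol's own definitions: exposure requires a public-system test, the comparator requires no contact, the outcome is visible only in public records, and the adjustment variables do not measure use of care. HZ ascertainment may therefore differ by exposure group and could bias the primary RR upward by the factor (1 − q1)/(1 − q0).

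The size is undetermined. A net gap of 2% to 5%, which is an assumption, gives a spurious RR of 1.02 to 1.05. That is small in absolute terms but not negligible in a study designed around 1.1. If the shares are equal there is no bias. The documents do not support saying that the RR is certainly above 1 for this reason, or that the bias equals the target effect. This is a reason to add an inexpensive check; it does not invalidate the primary analysis.

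**What to change.** **Section 4.9.6.** Pre-specify a sensitivity analysis that compares lab-confirmed subjects with test-negative subjects:

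- Test-negative means at least one negative and no earlier positive PCR or antigen result in RedMIVA.
- Time runs from the first negative sample, with a switch to lab-confirmed status at a first positive.
- The comparison is stratified or matched on calendar month of testing.
- The result is reported beside the primary RR. If a raised primary RR shrinks materially here, it is interpreted cautiously.

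This should not become a rule that both estimates must lie on the same side of 1. When the true test-negative RR is 1, its estimate exceeds 1 about half the time, and the two estimates share the same exposed cases. Nor should the two be described as bracketing the effect, since that needs biases in opposite directions, which has not been shown.

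**Section 4.10.** State that the lack of information on non-users and private patients may fall unequally on the two groups.

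**Optional.** Restrict both groups to subjects with public-system contact before the pandemic. Annex 1 appears to limit visit data to HZ and comorbidity codes, so this may need a further data request.

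**Cost.** One added model and some wording, on data already requested. The section 4.9.4 totals give 2,112,504 − 288,311 = 1,824,193 negative tests in 2020 (tests, not persons). Tested people may be sicker or heavier users of care, so the comparison may be conservative. It is also less precise than using all SARS-CoV-2-free time. The loss need not be large, because the 770 exposed events dominate the variance. If comparator events fell to an assumed quarter (3,500), the SE of log RR would rise from √(1/770 + 1/14,000) = 0.0370 to √(1/770 + 1/3,500) = 0.0398.
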